14.2 Sample Size/Accrual Rate

14.2.1 Sample Size

CONFIDENTIAL

This document is confidential. Do not disclose or use except as authorized.

Phase II ECP and IL-2 for chronic GVHD
Version 2.0; August 15, 2016

The target accrual is 25 evaluable patients.

14.2.2 Accrual

Based on our prior studies of 07-083 and 11-149, we anticipate that the accrual will complete within two years. Patients will be followed for 12 months after completing study accrual.

Gender of subjects will not be used as a criterion for inclusion or exclusion in this study and there are no restrictions on the accrual of minorities. In 2013, 41% of all transplanted patients were women and approximately 10% of patients were minorities. Based on this self-reported ethnicity and gender in our transplant program in 2013, the anticipated accrual in subgroups defined by gender and race is summarized in the table below.

Accrual Targets					
Ethnic Category	Sex/Gender				
	Females		Males		Total
Hispanic or Latino	1	+	1	=	2
Not Hispanic or Latino	9	+	14	=	23
Ethnic Category: Total of all subjects	10	+	15	=	25
Racial Category					
American Indian or Alaskan Native	0	+	0	=	0
Asian	1	+	1	=	2
Black or African American	1	+	1	=	2
Native Hawaiian or other Pacific Islander	0	+	0	=	
White	8	+	13	=	21
Racial Category: Total of all subjects	10	+	15	=	25

14.3 Stratification Factors

N/A

14.4 Analysis of Secondary Endpoints

Secondary endpoints include toxicity, immunologic effects, prednisone use, overall survival, progression-free survival, non-relapse mortality, and relapse. All analyses will be reported descriptively. Predictors for response will be explored in univariable analysis, including the impact of number of prior cGVHD therapies.

CONFIDENTIAL

This document is confidential. Do not disclose or use except as authorized.

14.5 Monitoring for Adverse Events.

Adverse events will be monitored closely. The monitoring guidelines will serve as a trigger for consultation with the DF/HCC Data Safety and Monitoring Committee (DSMC) for additional review, and are not regarded as formal stopping rules that would mandate automatic closure of study enrollment. ECP+IL-2 treatment was well tolerated in the 4 DFCI patients treated thus far.

If in the first 10 patients who start the IL-2 treatment, we observe 3 or more patients with grade 3 or higher treatment related toxicity, further accrual will be halted pending review by the DSMC. Depending on the findings of its review, the DSMC may recommend the permanent closure of enrollment or continuation of enrollment. With this design, the probability of halting the enrollment is 0.07 if the true but unknown grade 3 or higher treatment related toxicity rate is 10%, 0.62 if the rate is 30%, and 0.95 if the rate is 50%.

The same rule will be applied to non-relapse mortality, relapse, and cGVHD progression.

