12.2 Safety Meetings

The DF/HCC Data and Safety Monitoring Committee (DSMC) will review and monitor toxicity and accrual data from this trial. The committee is composed of clinical specialists with experience in oncology and who have no direct relationship with the

CONFIDENTIAL

This document is confidential. Do not disclose or use except as authorized.

study. Information that raises any questions about participant safety will be addressed with the Principal Investigator and study team.

The DSMC will meet regularly to review toxicity and accrual data. Information to be provided to the committee may include: up-to-date participant accrual; current dose level information; DLT information; all grade 2 or higher unexpected adverse events that have been reported; summary of all deaths occurring within 30 days for Phase I or II protocols; for gene transfer protocols, summary of all deaths while being treated and during active follow-up; any response information; audit results, and a summary provided by the study team. Other information (e.g. scans, laboratory values) will be provided upon request.

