14. STATISTICAL CONSIDERATIONS

14.1 Study Design/Endpoints

This is a one-stage Phase II trial to assess the efficacy of 16 weeks extracorporeal photopheresis (ECP) with the addition of daily low-dose subcutaneous (SC) interleukin-2 (IL-2) for weeks 8-16 in patients with steroid-refractory chronic graft-versus-host disease (cGVHD). The primary endpoint is overall response as defined in Section 10.0. Response will be evaluated at 16 weeks of treatment.

Our previous studies of low-dose IL-2 alone (DFCI#07-083, 11-149) for steroid refractory cGVHD showed a overall response rate of ~50-60%, and a randomized phase 2 trial of ECP vs. placebo showed a 40% response rate of skin cGVHD and 33% response rate of non-skin cGVHD⁴³. Conservatively extrapolating this information, we would consider ECP+IL-2 potentially efficacious if the overall response rate is 75% or higher and unworthy if 50% or lower. With 25 evaluable patients, if 17 or more patients respond, the treatment will be considered efficacious for the treatment of steroid refractory cGVHD.

With this design, the probability of concluding the treatment efficacious is 0.85 if the true but unknown response rate is 75% and 0.05 if the true rate is 50%. This decision rule is calculated using the exact binomial method. Table 1 below presents the operating characteristics of this design. Patients will be considered evaluable for response if they receive at least one week of ECP, which we anticipate to occur to all patients based on our prior experience. Patient will be replaced if the patient is removed from the study for reasons unrelated to the treatment (see Section 5.4).

Table 1. Operating Characteristics

	True but Unknown Response Rate						
	50%	55%	60%	65%	70%	75%	
Prob(≥ 17 responses in 25)	0.05	0.13	0.27	0.47	0.68	0.85	

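### The single toxicity trigger in Section 14.5 ends at the tenth IL-2 starter; a second count at 20 would halve the chance of missing a 30% rate, at a small cost

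*Combined protocol and SAP*

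**What the plan says.** Section 14.5 has one numeric rule for toxicity. Its condition reads: "If in the first 10 patients who start the IL-2 treatment, we observe 3 or more patients with grade 3 or higher treatment related toxicity". When it is met, accrual halts pending DSMC review. The section gives halt probabilities of 0.07, 0.62 and 0.95 at true rates of 10%, 30% and 50%. It describes the guideline as a prompt for consulting the DSMC, not a rule that closes enrolment automatically. It applies the same rule to non-relapse mortality, relapse and progression of chronic graft-versus-host disease (cGVHD).

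Section 14.2.1 sets the size of the trial: "The target accrual is 25 evaluable patients". Section 12.2 describes the continuing oversight: "The DSMC will meet regularly to review toxicity and accrual data". It attaches no threshold to those meetings. Sections 5.4 and 6.2 give criteria for withholding or stopping IL-2 in an individual patient. Section 11.4.1 requires serious adverse events to be reported to the overall principal investigator within 24 hours, with a list of exempt Grade 4 events expected after transplantation.

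**The concern.** The numeric trigger covers the first 10 IL-2 starters and then lapses, with no reason given. Suppose 2 of the first 10 have a qualifying event and several of the next patients do too. Nothing in Section 14.5 then prompts a review, although the pooled count would by then be hard to ignore. Prior experience with the combination is 4 patients, so the trial itself will supply most of the safety information, and much of it will arrive after the tenth starter.

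At stake is whether a raised rate of severe treatment-related toxicity leads to a prompt, predefined review, or depends on someone noticing it at a scheduled meeting. The efficacy analysis is not affected.

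**Working it through.** **Inputs.** Rule: 3 or more of 10 (Section 14.5). Target: 25 evaluable patients (Section 14.2.1). Accrual: within two years (Section 14.2.2). IL-2 starts after week 8 of photopheresis and runs for 8 weeks (Section 5).

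**Step 1: reproduce the plan's figures.** P(halt) = 1 − Σ C(10,x) pˣ(1−p)¹⁰⁻ˣ for x = 0, 1, 2.

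- p = 0.10: 1 − (0.3487 + 0.3874 + 0.1937) = 0.0702 (stated 0.07)
- p = 0.30: 1 − (0.0282 + 0.1211 + 0.2335) = 0.6172 (stated 0.62)
- p = 0.50: 1 − (0.0010 + 0.0098 + 0.0439) = 0.9453 (stated 0.95)

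All three agree. At 30% the trigger is not met with probability 1 − 0.6172 = 0.3828.

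**Step 2: keep that rule and add 5 or more of the first 20.** The trial passes both rules if x ≤ 2 of the first 10 have events and fewer than 5 − x of the next 10 do:

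P(no trigger) = Σ (x = 0, 1, 2) P[Bin(10,p) = x] × P[Bin(10,p) ≤ 4 − x].

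At p = 0.30: 0.0282 × 0.8497 + 0.1211 × 0.6496 + 0.2335 × 0.3828 = 0.0240 + 0.0786 + 0.0894 = 0.1920.

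| True rate | P(halt), current rule | P(halt), with added trigger |
|---|---|---|
| 10% | 0.070 | 0.089 |
| 20% | 0.322 | 0.456 |
| 30% | 0.617 | 0.808 |
| 40% | 0.833 | 0.961 |
| 50% | 0.945 | 0.996 |

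**Step 3: neighbouring thresholds at 20 starters.** With 4 or more, the chance of no trigger at 30% is 0.100, but the halt probability at 10% rises to 0.153. With 6 or more, the figures are 0.281 and 0.073. Five lies between: 0.192 and 0.089.

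**Step 4: timing.** Assume 25 patients enrol evenly over 24 months, or 25/24 ≈ 1.04 per month, and that all start IL-2. The 20th enrols at about month 20 × 0.96 = 19.2. That patient completes 16 weeks (about 3.7 months) at about month 22.9, when 22.9 × 25/24 ≈ 23.8 patients are due to have enrolled. Waiting for 20 completed courses therefore leaves only about 1 to 2 patients to enrol.

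If the trigger instead acts at the fifth event, it comes earlier. A simulation at a 30% rate, with event times uniform over the 8-week IL-2 course, looked at trials in which the added trigger fires after the first was missed. When it fires, a median of about 5 patients are not yet enrolled and 7 have not started IL-2.

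**The case against.** The strongest reply is that nothing here is wrong. The 0.62 at 30% is printed in the plan, so the complementary 0.38 is a disclosed choice for a consultation trigger. This stands, and it is why the point is an improvement only.

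Three stronger readings are tempting, and the documents do not support them:

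- **That later patients have no protection.** They keep the individual criteria of Sections 5.4 and 6.2, serious adverse event reporting and DSMC review. Only a numeric cohort-level trigger is missing.
- **That the rule is underpowered for the rates it was built to detect.** Section 14.5 names no unacceptable rate. The 10%, 30% and 50% are illustrations, and at 50% the rule triggers with probability 0.95.
- **That the earlier trial showed IL-2 alone causing thrombotic microangiopathy.** Section 6.1.1 calls the two cases possibly related and notes that both patients were taking a calcineurin inhibitor and sirolimus. Sections 3.2.2 and 3.2.3 exclude that concurrent use and any history of the condition. The study calendar adds targeted laboratory tests soon after IL-2 starts, and Section 6.2 has a discontinuation criterion for it.

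The benefit is also modest when counted in patients. The extra probability of triggering at 30% is 0.808 − 0.617 = 0.191. With about 5 patients left to enrol when it fires, that averages about 0.191 × 5 ≈ 1 fewer patient enrolled per trial, if the pause becomes permanent. The threshold of 5 of 20 is one reasonable choice among several. These limits stand, but they do not explain why the trigger should lapse at 10 when extending it costs so little.

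**Conclusion.** The point holds as a design improvement. The chance that a true 30% rate meets no numeric trigger falls from 0.38 to 0.19, and at 40% it falls from 1 − 0.833 = 0.167 to 1 − 0.961 = 0.039. Not meeting the trigger means that no predefined review is prompted. It does not mean that the events go unseen.

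The probabilities assume independent events with a common rate. The figure of 15 uncovered patients (25 − 10) assumes that every accrued patient starts IL-2. The plan does not guarantee this. Section 14.1 says "Patients will be considered evaluable for response if they receive at least one week of ECP", Section 10 asks for at least 4 weeks of the combination, and Section 14.1 allows replacement, so the number could be somewhat lower or higher. The timing result rests on the accrual and event-time assumptions stated with it.

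**What to change.** Add to Section 14.5: *The same DSMC review is triggered as soon as a fifth patient among the first 20 who start IL-2 has grade 3 or higher treatment-related toxicity.*

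State that this added trigger applies to treatment-related toxicity only. Otherwise the existing sentence that carries the rule over to non-relapse mortality, relapse and cGVHD progression becomes ambiguous. If the sponsor wants the trigger for those endpoints too, give operating characteristics for them, since false pauses would accumulate over four endpoints.

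Report the combined halt probabilities at 10% to 50% beside the current ones, and state the downsides openly:

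- more pauses at rates of 10% and 20%, which the plan does not call unacceptable;
- no numeric trigger for starters 21 to 25;
- little benefit unless the review is called when the fifth event occurs.

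The cost is a sentence or two, a small table and a running count supplied to a committee that already meets. No patients are added, the trigger remains a prompt for consultation, and the 17-of-25 efficacy rule is unchanged.

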15. PUBLICATION PLAN

The initial study results will be made public within 12 months of the end of data collection. The study report is planned for publication in a peer-reviewed journal, and the initial release may be an abstract that meets the requirements of the International Committee of Medical Journal Editors. A final report of study outcomes will be made public no later than 3 years after the end of data collection.

The study PI holds the primary responsibility for publication of study results. Permission of the study PI will be required before any unpublished study information can be used or passed on to a third party.

CONFIDENTIAL

This document is confidential. Do not disclose or use except as authorized.

17. APPENDICES

CONFIDENTIAL

This document is confidential. Do not disclose or use except as authorized.

Phase II ECP and IL-2 for chronic GVHD**Version 2.0; August 15, 2016****17.1 Appendix A: PERFORMANCE STATUS**

ECOG Performance Status Scale		Karnofsky Performance Scale	
Grade	Description	Percent	Description
0	Normal activity. Fully active, able to carry on all pre-disease performance without restriction.	100	Normal, no complaints, no evidence of disease.
		90	Able to carry on normal activity; minor signs or symptoms of disease.
1	Symptoms, but ambulatory. Restricted in physically strenuous activity, but ambulatory and able to carry out work of a light or sedentary nature (e.g., light housework, office work).	80	Normal activity with effort; some signs or symptoms of disease.
		70	Cares for self, unable to carry on normal activity or to do active work.
2	In bed < 50% of the time. Ambulatory and capable of all self-care, but unable to carry out any work activities. Up and about more than 50% of waking hours.	60	Requires occasional assistance, but is able to care for most of his/her needs.
		50	Requires considerable assistance and frequent medical care.
3	In bed >50% of the time. Capable of only limited self-care, confined to bed or chair more than 50% of waking hours.	40	Disabled, requires special care and assistance.
		30	Severely disabled, hospitalization indicated. Death not imminent.
4	100% bedridden. Completely disabled. Cannot carry on any self-care. Totally confined to bed or chair.	20	Very sick, hospitalization indicated. Death not imminent.
		10	Moribund, fatal processes progressing rapidly.
5	Dead.	0	Dead.

CONFIDENTIAL

This document is confidential. Do not disclose or use except as authorized.

17.2 Appendix B: BODY SURFACE AREA AND CREATININE CLEARANCE

Body surface area (BSA) should be calculated using Dubois formula that yields the following results in meters squared (m²):

$$\text{BSA} = (W^{0.425} \times H^{0.725}) \times 0.007184$$

where the weight is in kilograms and the height is in centimeters.

Creatinine clearance (CrCl) can be calculated using the Cockcroft-Gault equation as follows:

$$\text{CrCl (ml/min)} = \frac{(140 - \text{age}) (\text{actual wt in kg})}{72 \times \text{serum creatinine (mg/dl)}}$$

For females, use 85% of calculated CrCl value.

Note: In markedly obese patients, the Cockcroft-Gault formula will tend to overestimate the creatinine clearance. (Adipose tissue tends to contribute little creatinine requiring renal clearance.)

CONFIDENTIAL

This document is confidential. Do not disclose or use except as authorized.

17.3 Appendix C: New York Heart Association Classification of Heart Disease

The following table presents the NYHA classification of cardiac disease.

Class	Functional Capacity	Objective Assessment
I	Patients with cardiac disease but without resulting limitations of physical activity. Ordinary physical activity does not cause undue fatigue, palpitation, dyspnea, or anginal pain.	No objective evidence of cardiovascular disease.
II	Patients with cardiac disease resulting in slight limitation of physical activity. They are comfortable at rest. Ordinary physical activity results in fatigue, palpitation, dyspnea, or anginal pain.	Objective evidence of minimal cardiovascular disease.
III	Patients with cardiac disease resulting in marked limitation of physical activity. They are comfortable at rest. Less than ordinary activity causes fatigue, palpitation, dyspnea, or anginal pain.	Objective evidence of moderately severe cardiovascular disease.
IV	Patients with cardiac disease resulting in inability to carry on any physical activity without discomfort. Symptoms of heart failure or the anginal syndrome may be present even at rest. If any physical activity is undertaken, discomfort is increased.	Objective evidence of severe cardiovascular disease.

Source: The Criteria Committee of New York Heart Association. Nomenclature and Criteria for Diagnosis of Diseases of the Heart and Great Vessels. 9th Ed. Boston, MA: Little, Brown & Co; 1994:253-256.

CONFIDENTIAL

This document is confidential. Do not disclose or use except as authorized.

17.4 Appendix D: DEFINITE AND PROBABLE cGVHD MANIFESTATIONS

Organ System	Definite manifestations of chronic GVHD	Possible manifestations of chronic GVHD
Skin	Scleroderma (superficial or fasciitis), lichen planus, vitiligo, scarring alopecia, hyperkeratosis pilaris, contractures from skin immobility, nail bed dysplasia	Eczematoid rash, dry skin, maculopapular rash, hair loss, hyperpigmentation
Mucous membranes	Lichen planus, non-infectious ulcers, corneal erosions/non-infectious conjunctivitis	Xerostomia, keratoconjunctivitis sicca
GI tract	Esophageal strictures, steatorrhea	Anorexia, malabsorption, weight loss, diarrhea, abdominal pain
Liver	None	Elevation of alkaline phosphatase, transaminitis, cholangitis, hyperbilirubinemia
GU tract	Vaginal stricture, lichen planus	Non-infectious vaginitis, vaginal atrophy
Musculoskeletal /Serosa	Non-septic arthritis, myositis, myasthenia, polyserositis, contractures from joint immobilization	Arthralgia
Hematologic	None	Thrombocytopenia, eosinophilia, autoimmune cytopenias
Lung	Bronchiolitis obliterans	Bronchiolitis obliterans with organizing pneumonia, interstitial pneumonitis

CONFIDENTIAL

This document is confidential. Do not disclose or use except as authorized.

Phase II ECP and IL-2 for chronic GVHD
Version 2.0; August 15, 2016

17.5 Appendix E: CHRONIC GVHD SYMPTOM SCORING SCALE

Name:

MRN:

Signature:

Date:

Have you had any of the following problems in the past 2 weeks?

	Not at all	Slightly	Moderately	Quite a bit	Extremely
SKIN:					
a. Abnormal skin color	0	1	2	3	4
b. Rashes	0	1	2	3	4
c. Thickened skin	0	1	2	3	4
d. Sores on skin	0	1	2	3	4
e. Itchy skin	0	1	2	3	4
EYES AND MOUTH:					
f. Dry eyes	0	1	2	3	4
g. Need to use eye drops frequently	0	1	2	3	4
h. Difficulty seeing clearly	0	1	2	3	4
i. Need to avoid certain foods due to mouth pain	0	1	2	3	4
j. Ulcers in mouth	0	1	2	3	4
k. Receiving nutrition from an intravenous line or feeding tube	0	1	2	3	4
BREATHING:					
l. Frequent cough	0	1	2	3	4
m. Colored sputum	0	1	2	3	4
n. Shortness of breath with exercise	0	1	2	3	4
o. Shortness of breath at rest	0	1	2	3	4
p. Need to use oxygen	0	1	2	3	4
EATING AND DIGESTION:					
q. Difficulty swallowing solid foods	0	1	2	3	4
r. Difficulty swallowing liquids	0	1	2	3	4
s. Vomiting	0	1	2	3	4

CONFIDENTIAL

This document is confidential. Do not disclose or use except as authorized.

Phase II ECP and IL-2 for chronic GVHD**Version 2.0; August 15, 2016**

t. Weight loss	0	1	2	3	4
	Not at all	Slightly	Moderately	Quite a bit	Extremely
MUSCLES AND JOINTS:					
u. Joint and muscle aches	0	1	2	3	4
v. Limited joint movement	0	1	2	3	4
w. Muscle cramps	0	1	2	3	4
x. Weak muscles	0	1	2	3	4
ENERGY:					
y. Loss of energy	0	1	2	3	4
z. Need to sleep more/take naps	0	1	2	3	4
Aa. Fevers	0	1	2	3	4
MENTAL AND EMOTIONAL:					
Bb. Depression	0	1	2	3	4
Cc. Anxiety	0	1	2	3	4
Dd. Difficulty sleeping	0	1	2	3	4

CONFIDENTIAL

This document is confidential. Do not disclose or use except as authorized.

17.6 Appendix F: cGVHD PARTIAL RESPONSE CRITERIA

Suggested calculations for partial organ response in cGVHD

Organ and Starting Score or Value	Partial Response Criterion*
Skin (percent of body surface)	
> 50 %	$e/s \leq 0.5$ and $e > 0$
25 – 50 %	$s - e \geq 25$ and $e > 0$
< 25 %	only CR; no PR possible
Platelet count	$e - s \geq 100,000/\mu L$ and $e < LLN$
Gastrointestinal (and other 0 – 3 scales)	
3	$e = 1$ or 2
2	$e = 1$
1	only CR; no PR possible
Liver function tests (ALT, alkaline phosphatase and bilirubin)	
$\geq 3x ULN$	$e/s \leq 0.5$ and $e > ULN$
< 3x ULN	only CR; no PR possible

*s, starting score or value; e, ending score or value; ULN, upper limit of normal; LLN, lower limit of normal

Examples

1. Skin: start score = 85, end score = 30; $e/s = 30/85 = 0.35 = PR$
2. Skin: start score = 65, end score = 45; $e/s = 45/65 = 0.75 = \text{not PR}$
3. Skin: start score = 45, end score = 15; $s - e = 30 = PR$
4. Skin: start score = 30, end score = 15; $s - e = 15 = \text{not PR}$

CONFIDENTIAL

This document is confidential. Do not disclose or use except as authorized.

17.7 Appendix G: cGVHD PROGRESSION CRITERIA

Suggested calculations for organ progression in cGVHD

Organ and Starting Score or Value	Progression Criterion*
Skin (percent of body surface)	$e - s \geq 25$
Platelet count	$s - e \geq 50,000/\mu L$ and $e < LLN$
Gastrointestinal (and other 0 – 3 scales)	$e - s \geq 1$
Liver (ALT, alkaline phosphatase and bilirubin) $s \geq 3 \times ULN$ $s < 3 \times ULN$	$e - s \geq 3 \times ULN$ $e - s \geq 2 \times ULN$
Lungs (12-point Lung Function Scale)¶	$e - s \geq 3^{\dagger}$

*s, starting score or value; e, ending score or value; ULN, upper limit of normal

¶The lung function scale is the sum of the FEV1 and DLCO (corrected for Hb) scores, each computed as: > 80% of predicted = 1; 70-79% = 2; 60-69% = 3; 50-59% = 4; 40-49% = 5; <40% = 6.

†If the starting lung function score is ≥ 10 , progression is defined as $\geq 5\%$ decrease of FEV1 in two tests measured at least 2 weeks apart. This time interval was selected because these syndromes can progress rapidly.

CONFIDENTIAL

This document is confidential. Do not disclose or use except as authorized.

17.8 Appendix H: NCI COMMONTOXICITY CRITERIA

[figure not shown]
Please refer to the CTEP website: <http://ctep.cancer.gov/reporting/ctc.html>
Forms available upon request.

CONFIDENTIAL

This document is confidential. Do not disclose or use except as authorized.

